The Investigator should be prepared to provide subject information, including, but not limited to: age, body weight, clinical presentation (ACS or stable coronary disease), CrCL using Cockcroft-Gault formula and CKD-EPI Equation for estimating GFR on the Natural Scale (see Section 17.6) and whether the subject is taking certain concomitant P-gp inhibitors (see Section 5.3.1).

Randomization is stratified by clinical presentation (ACS or stable coronary disease), requirement for dose adjustment of edoxaban (60 or 30 mg), and geographical region. Subjects are assigned randomly via the above mentioned IXRS such that the study has a 1:1 ratio of subjects in the two antithrombotic treatment regimens:

- Edoxaban-based regimen for 12 months:

1. Edoxaban 60 mg once-daily or 30 mg once-daily in selected subjects (see below "Dosage Form, Dose, and Route of Administration" and Section 5.3.1).
2. Clopidogrel 75mg once-daily (or in the presence of a documented clinical need prasugrel [5mg or 10 mg once-daily] / ticagrelor [90 mg twice-daily] may be used).

The use of a P2Y₁₂ antagonist other than clopidogrel must be pre-declared.

3. Concomitant use of another anti-platelet agent (i.e. ASA) is **not** allowed.

- VKA-based regimen for 12 months:

1. The VKA of choice with once-daily dosing for target international normalized ratio (INR) between 2.0 to 3.0, inclusive.
2. Clopidogrel 75mg once-daily (or in the presence of a documented clinical need prasugrel [5mg or 10 mg once-daily] / ticagrelor [90 mg twice-daily] may be used).

3. ASA (100 mg once-daily) for a minimum of 1 month and up to 12 months duration at the Investigator discretion guided by the clinical presentation (ACS or stable coronary disease), and upon the CHA₂DS₂-VASc and HAS-BLED score. (1}

4. If the use of a P2Y₁₂ antagonist other than clopidogrel must be pre-declared, together with the intended duration of ASA treatment.

All dosage adjustments are implemented through the IXRS. The IXRS provides the appropriate drug supply kit number based on the subject's information as provided by the Investigator.

Note: For simplicity, this protocol uses the term "edoxaban" to refer to edoxaban tosylate, "clopidogrel" to refer to clopidogrel bisulfate and the term " prasugrel" to refer to prasugrel hydrochloride.

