VKA is supplied as commercially available tablets of the preferred VKA for each selected country participating in the study, being either:

- Warfarin: 1 and 2.5 mg tablets.
- Phenprocoumon: 3 mg tablets.
- Fluindione: 20 mg tablets(exclusive to France).
- Acenocoumarol: 4 mg tablets.

The Investigator monitors the INR and adjusts the VKA dose to maintain the INR within target. It is the Investigator's responsibility to collect monthly INR assessments and record these throughout the study.

P2Y₁₂ antagonist:

- Clopidogrel 75 mg, oral commercially available tablets.

Subjects receive clopidogrel 75 mg once-daily according to the prescribing information, or in the presence of a documented clinical need (e.g. but not restricted to known clopidogrel non-responder), either

- o Prasugrel 5 or 10 mg, oral commercially available tablets.

Subjects receive prasugrel 10 mg once-daily or prasugrel 5 mg once-daily if ≥ 75 years of age or ≥ 60 kg (132 lb), according to the prescribing information.

- o Ticagrelor 90 mg, oral commercially available tablets.

Subjects receive ticagrelor 90 mg twice-daily according to the prescribing information.

Aspirin (ASA): 100 mg, oral commercially available tablets.

Subjects assigned to the VKA-based regimen receive 100 mg once-daily of ASA. In subjects assigned to the edoxaban-based regimen ASA is not allowed.

Sponsor supplies participating sites with study medication, consisting of edoxaban, VKA (country pre-defined), P2Y₁₂ antagonist (clopidogrel, prasugrel or ticagrelor), and ASA. Please refer to the local SmPC or IB for edoxaban as applicable and to the SmPC of each other study medication.

All dosage adjustments are implemented through the IXRS. The IXRS provides the appropriate drug supply kit number based on the subject's information as provided by the Investigator.

Study Endpoints:

Primary endpoint:

The primary endpoint is the composite of major or clinically relevant non-major bleeding (MCRB) defined according to the ISTH bleeding definitions, analyzed as time to first occurrence of any component.

Secondary endpoints are defined as:

- Main efficacy endpoint (MEE), defined as the composite of cardiovascular (CV) death, stroke, systemic embolic events (SEE), spontaneous myocardial infarction (MI) and definite stent thrombosis (as per ARC consensus definitions).
- Net clinical benefit (NCB), defined as the composite of CV death, stroke, SEE, spontaneous MI, definite stent thrombosis and ISTH-defined major bleeding.

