3. STUDY DESIGN

3.1. Overall Plan

This is a multinational, multicenter, randomized, open-label Phase 3b study with blinded evaluation of endpoints by an independent CEC (PROBE design). At least 150 sites will be required to enroll 1500 subjects (750 subjects per antithrombotic regimen) in Europe, and Asia-Pacific

A schematic presentation of the study design is provided in Figure 3.1.

The study is divided into a screening period (incl. pre-screening), a treatment period and an observational post-treatment follow-up period. The screening period starts after a percutaneous coronary intervention (PCI) with stent placement. Subjects with an OAC indication for AF for at least 12 months who have successfully undergone a PCI and who received a stent are eligible for inclusion in the study.

Subjects should satisfy the pre-screening criteria before IC is signed. Once written, IC is obtained, and eligibility criteria (inclusion and exclusion) are met subjects are randomized without delay (1:1 ratio), to one of two treatment groups being an edoxaban-based regimen (index regimen) and a VKA-based regimen (control regimen). Consenting and randomization takes place within 4 hours and 5 days post-PCI and before hospital discharge. If a staged PCI is planned, consenting and randomization takes place after successful completion of the last stage.

[figure not shown]
The edoxaban-based regimen consists of treatment with edoxaban 60 mg once-daily and clopidogrel 75 mg once-daily (or in the presence of a documented clinical need prasugrel [5 or 10 mg once-daily] /or ticagrelor [90 mg twice-daily]) for 12 months.

The VKA-based regimen, dosed to achieve a target INR of 2.0- 3.0, in combination with clopidogrel 75 mg once-daily (or in the presence of a documented clinical need prasugrel [5 or 10 mg once-daily] /or ticagrelor (90 mg twice-daily)) for 12 months and ASA (100 mg once-daily) for 1-12 months. These regimens are detailed in Section 5. The assigned regimen is implemented after randomization without any due delay (please refer to Section 5). The randomized regimens (edoxaban-based or VKA-based) and clopidogrel (or other P2Y12 antagonist) are continued for 12 months, when the scheduled end-of-treatment (EOT) is reached.

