5.2. Study Treatment Regimens

5.2.1. Edoxaban-based regimen for 12 months

- Edoxaban 60 mg once-daily or 30 mg once-daily in selected subjects (see Section 5.3.1).
- Clopidogrel 75 mg once-daily (or in the presence of a documented clinical need prasugrel [5mg or 10 mg once-daily] or ticagrelor [90 mg twice-daily] may be used).
- The use of a P2Y₁₂ antagonist other than clopidogrel must be pre-declared.
- Concomitant use of another anti-platelet agent (i.e. ASA) is not allowed.

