5.2.2. VKA-based regimen for 12 months (control regimen)

- Oral VKA of choice with dosing for target international normalized ratio (INR) between 2.0 - 3.0, inclusive.
- Clopidogrel 75mg once-daily (or in the presence of a documented clinical need prasugrel [10 mg once-daily]/ ticagrelor [90 mg twice-daily] may be used).
- ASA (100 mg once-daily) for a minimum of 1 month and up to 12 months duration at the Investigator discretion guided by the clinical presentation

(ACS or stable CAD), and upon the CHA2DS2-VASc and HAS-BLED score (1).

- The use of a P2Y₁₂ antagonist other than clopidogrel must be pre-declared, together with the intended duration of ASA treatment.

For simplicity, this protocol uses the term "edoxaban" to refer to edoxaban tosylate, "clopidogrel" to refer to clopidogrel bisulfate and the term "prasugrel" to refer to prasugrel hydrochloride.

Pre-declaration means that the Investigator specifies this information in the IXRS, prior to randomization and assignment to an antithrombotic regimen.

3. Edoxaban

Edoxaban tosylate (DU-176b, trade names Lixiana®, Savaysa®), referred throughout this protocol by the term "edoxaban" for simplicity, is part of the edoxaban-based regimen. Please refer to Section 5.9 Labeling and Packaging.

According to local SmPC or 1B as applicable, subjects may take edoxaban with or without food, in the morning or evening, but at approximately the same time every day.

If a dose of edoxaban is missed, the dose must be taken as soon as possible as long as on the same day. The dose of edoxaban must not be doubled to make up for a missed dose.

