5.5.1. Dose

Clopidogrel bisulfate 75mg once-daily as provided by sponsor.

In the presence of a documented clinical need (e.g. known hypersensitivity to clopidogrel or its excipients, known CYP2C19 poor metabolizer-clopidogrel non-responder, among others) the use of a P2Y₁₂ antagonist other than clopidogrel is allowed but must be pre-declared prior to randomization.

Either prasugrel [5 or 10 mg once-daily] or ticagrelor [90 mg twice-daily] may be used according to the regional clinical practice guidelines for the dose and administration of the respective P2Y₁₂ antagonist. The Investigator should follow

the relevant SmPC and the applicable regional guidelines regarding dose and transition from or to another P2Y₁₂ antagonist.

The 5 mg once-daily dose of prasugrel should be given as maintenance dose in subjects with body weight < 60 kg. The use of prasugrel in subjects > 75 years of age is generally not recommended but if treatment is deemed necessary, then a reduced maintenance dose of 5 mg once-daily should be prescribed in subjects in this age group. For additional details please consult the SmPC and the drug-- package insert.

Both prasugrel 5 or 10 mg once-daily and ticagrelor 90 mg twice-daily will be provided by the sponsor and dispensed through the IXRS. The Investigator or designee is responsible for dispensing the P2Y₁₂ antagonist through the IXRS and must ensure that drug supplied by sponsor is used only in accordance with the protocol and to the drug package insert.

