5.9.3. P2Y₁₂ antagonist

Sponsor provides the P2Y₁₂ antagonists which is packaged in monthly wallets with blisters. Materials are supplied in their original primary packaging and labelled with a single panel multilingual booklet.

Clopidogrel will be supplied as commercially available 75 mg film-coated tablets. In addition, prasugrel and ticagrelor will also be provided for subjects with a documented clinical need and as pre-declared at randomization. Prasugrel will be supplied as commercially available 5 mg film-coated tablets. Ticagrelor will be supplied as commercially available 90 mg film-coated tablets.

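### The prasugrel instructions conflict: Section 5.2.2 omits the 5 mg strength for the VKA arm only, and the dose criteria and tablet supply differ between sections

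*Combined protocol and SAP*

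**What the plan says.** **Permitted strength by arm.** For the edoxaban arm, protocol Section 5.2.1 says that "in the presence of a documented clinical need prasugrel [5mg or 10 mg once-daily] or ticagrelor [90 mg twice-daily] may be used". For the VKA arm, Section 5.2.2 says that "in the presence of a documented clinical need prasugrel [10 mg once-daily]/ ticagrelor [90 mg twice-daily] may be used". The synopsis uses one wording for both regimens, the VKA regimen included: "in the presence of a documented clinical need prasugrel [5mg or 10 mg once-daily] / ticagrelor [90 mg twice-daily] may be used". Section 3.1 describes the VKA regimen as "in combination with clopidogrel 75 mg once-daily (or in the presence of a documented clinical need prasugrel [5 or 10 mg once-daily", that is, with both strengths. The Figure 3.1 notes make no distinction by arm. Section 5.5, which states that it applies to both regimens, allows 5 or 10 mg in Section 5.5.1.

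**Criteria for the 5 mg dose.** The synopsis reads, as extracted: "Subjects receive prasugrel 10 mg once-daily or prasugrel 5 mg once-daily if ≥ 75 years of age or ≥ 60 kg (132 lb". Section 5.5.1 reads: "The 5 mg once-daily dose of prasugrel should be given as maintenance dose in subjects with body weight < 60 kg". On age, Section 5.5.1 says: "The use of prasugrel in subjects > 75 years of age is generally not recommended", with 5 mg if treatment is judged necessary.

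**Supply.** Section 5.9.3 says: "Prasugrel will be supplied as commercially available 5 mg film-coated tablets". The synopsis lists tablets of 5 or 10 mg, and Section 5.5.1 says that the sponsor provides both and that they are dispensed through the IXRS.

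**The concern.** P2Y12 treatment is common to both regimens, and the primary endpoint is major or clinically relevant non-major bleeding. Sections 5.2.1 and 5.2.2 are the sections that define the two randomised regimens, so a difference between them in permitted antiplatelet strength stands out. A site that took Section 5.2.2 at its word would have no 5 mg option for a VKA subject, while the same subject in the edoxaban arm could receive it.

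Treatment is open-label and only adjudication is blinded. Pre-declaration covers the choice of an agent other than clopidogrel; the documents do not say that the prasugrel dose is pre-declared. Section 5.5.3 also allows a change of P2Y12 agent after randomisation for a non-bleeding side effect, with prasugrel as its example, so some prasugrel doses would be set with the arm known. The Cox model in Section 11.4 adjusts for the stratification factors, and P2Y12 agent and dose are not among them.

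**Working it through.** **1. The plan's own figures.** Section 11.9 assumes one-year event rates of 24% (VKA) and 18% (edoxaban).

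- HR = ln(1 − 0.18) / ln(1 − 0.24) = 0.7231, as stated.
- Events for 80% power at two-sided 0.05 (Schoenfeld) = (1.960 + 0.842)² / (0.25 × ln(0.7231)²) = 298.7, so 299. Subjects per arm = 299 / (0.24 + 0.18) = 712, as stated.
- Non-inferiority at 750 per arm, true HR 0.88, margin 1.20: edoxaban rate = 1 − 0.76^0.88 = 0.2146; events = 750 × (0.24 + 0.2146) = 340.9; power = Φ(√(340.9/4) × ln(1.20/0.88) − 1.960) = 81.7%, against 82% stated.

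No prasugrel quantity enters any of these, so none changes.

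**2. The passages side by side.**

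| Place | Strengths for VKA arm | Criterion for 5 mg | Tablets supplied |
|---|---|---|---|
| Synopsis, study design | 5 or 10 mg | none given | – |
| Synopsis, dosage text | 5 or 10 mg, no arm difference | age ≥ 75 or weight ≥ 60 kg (as extracted) | 5 or 10 mg |
| 3.1 and Figure 3.1 notes | 5 or 10 mg | none given | – |
| 5.2.1 (edoxaban arm) | not applicable; 5 or 10 mg for edoxaban | none given | – |
| 5.2.2 | 10 mg only | none given | – |
| 5.5.1 (both arms) | 5 or 10 mg | weight < 60 kg; age > 75 if used at all | 5 and 10 mg |
| 5.9.3 | – | – | 5 mg only |

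**3. What the texts give for three subjects using prasugrel.**

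- *78 years, 80 kg.* The synopsis dosage text gives 5 mg. Section 5.5.1 also leads to 5 mg if prasugrel is used. Section 5.2.1 permits that in the edoxaban arm; Section 5.2.2 lists only 10 mg in the VKA arm. This case does not depend on the weight sign.
- *70 years, 58 kg.* The synopsis as extracted gives 10 mg, since neither criterion is met; Section 5.5.1 gives 5 mg. This depends on the weight sign.
- *60 years, 80 kg.* The synopsis as extracted gives 5 mg; Section 5.5.1 triggers no reduction from 10 mg. This too depends on the weight sign.

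The two age criteria differ on dose only at exactly 75 years.

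**4. Possible size of the effect (illustration only).** The documents give neither prasugrel use nor a dose–bleeding relation. Let s be the share of VKA-arm subjects who would otherwise receive 5 mg but are given 10 mg, and m the factor by which this multiplies their bleeding hazard; both are assumptions. The VKA one-year rate becomes p = (1 − s) × 0.24 + s × (1 − 0.76^m), and a true HR of 1.00 appears as about ln(0.76) / ln(1 − p).

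| s | m | p | Apparent HR |
|---|---|---|---|
| 1% | 1.25 | 0.2405 | 0.998 |
| 2% | 1.5 | 0.2419 | 0.991 |
| 5% | 1.5 | 0.2449 | 0.977 |
| 5% | 2 | 0.2491 | 0.958 |
| 10% | 2 | 0.2582 | 0.919 |

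Shares of 1% and 5% of 750 are about 8 and 38 subjects. These must all be VKA subjects who would otherwise take 5 mg, which is a subset of the VKA-arm prasugrel users.

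**The case against.** The strongest defence is that the dose is governed elsewhere, and identically for both arms. Section 5.5.1 is the dedicated dose section, covers both regimens, points to the product label and regional guidelines, and routes dispensing through the IXRS. The bullets in Sections 5.2.1 and 5.2.2 are permissive summaries. The Section 5.2.2 bracket matches the synopsis entry for the VKA arm except for the missing 5 mg. Words are lost elsewhere too: the primary objective in Section 2.1.1 lacks the VKA comparator that the synopsis contains. All this makes an incomplete line the likeliest explanation. That stands, and a reader who infers a deliberate difference between the arms goes beyond the documents.

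A reader might also infer that the higher strength is reserved for the control arm. It is not: Section 5.2.1 permits 10 mg with edoxaban. What Section 5.2.2 lacks is the lower strength.

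The opposite weight rules invite the inference of an established safety conflict. The reviewed text does not support that yet. Comparison signs are visibly corrupted in several places (Sections 5.4.3, 9.3.1 and 17.4, and the schedule footnotes), so the synopsis signs need checking on the original page.

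Finally, counting four rival dosing rules overstates the matter. Listing 5 or 10 mg is compatible with Section 5.5.1, and Section 5.9.3 concerns tablet strength: 10 mg could be made up from 5 mg tablets. No section says so, however, and Section 5.8 assesses P2Y12 compliance by tablet count, so the supply text still needs aligning.

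**Conclusion.** The contradiction in permitted strengths between Section 5.2.2 and the other sections is plain wording and rests on no inequality sign. The supply conflict between Section 5.9.3 and both the synopsis and Section 5.5.1 is equally plain. The weight-criterion conflict is conditional on the synopsis signs being as extracted.

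It would be too strong to conclude that the primary comparison is biased. A bias arises only if sites or the IXRS follow Section 5.2.2 over Section 5.5.1, only among VKA subjects who would otherwise take 5 mg, and only if the higher dose causes more bleeding, which is assumed here. Under those conditions it would run in favour of edoxaban. Its size cannot be derived from the documents and is likely small, as the illustration shows unless the affected share reaches several percent. The design's alpha, power and sample size are untouched.

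This is a minor to moderate inconsistency in dosing instructions. The case for correcting it rests on clear instructions and symmetry between arms for a bleeding-relevant drug, more than on any expected shift in the hazard ratio.

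**What to change.** - Check the synopsis inequality signs against the original page.
- Reconcile the synopsis (study design and dosage text), Section 3.1, the Figure 3.1 notes and Sections 5.2.1, 5.2.2 and 5.5.1 into one prasugrel text that applies identically to both arms. State the weight and age criteria once and cross-refer to them elsewhere.
- Make the Section 5.9.3 supply list match the strengths that this text needs.
- Confirm that the IXRS specification applies the same rule in both arms.

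Which dose and cut-offs are right is for the sponsor to decide; this review takes no position. The cost is a wording amendment and a specification check, with no additional subjects, visits or tests.

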5.3.1. Dose

Edoxaban 60 mg once-daily.

At randomization, the recommended dose of edoxaban is 30 mg once-daily in subjects with 1 or more of the following factors:

- Moderate or severe renal impairment (calculated CrCL 15 - 50 mL/min),
- Low body weight of < 60 kg (132 lbs),
- Concurrent use of P-gp inhibitors (please refer to local SmPC or to 1B, as applicable).

In EU countries, according to SmPC concomitant use of edoxaban with cyclosporine, dronedarone, erythromycin, or ketoconazole requires dose reduction to 30 mg once-daily. Concomitant use of edoxaban with quinidine, verapamil, or amiodarone does not require dose reduction.

All edoxaban dosage adjustments will be implemented through the IXRS. The IXRS will provide the appropriate drug supply kit number.

If low body weight (< 60 kg) present at randomization, the edoxaban dose is reduced permanently and even if the subject gains weight, the edoxaban dose remains reduced.

The dose of edoxaban returns to the regular dosage regimen of 60 mg once-daily any time the subject no longer displays any of the other above mentioned factors.

After randomization and in subjects without dose reduction, if subject's:

body weight drops to < 60 kg and the body weight change is > 10% of the subject's baseline body weight, then the edoxaban dose is reduced (i.e., to 30 mg once-daily) permanently.

CrCL becomes 15 to 50 mL/min and the CrCL change is > 20% of the subject's baseline CrCL, then the edoxaban dose is reduced.

Develops the need for concomitant treatment with certain P-gp inhibitors which require edoxaban dose adjustment, then the edoxaban dose is reduced (i.e., to 30 mg once-daily).

The dose of 15 mg edoxaban once-daily is not indicated as monotherapy and is solely provided as part of transition from edoxaban 30 mg at the end of study (see Section 5.3.3).

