18. Currently participating in another clinical trial that potentially interferes with the current study;
 19. Previous randomization in this study;
 20. Active on prescription drug abuse and addiction; abuse of illicit substances (i.e. marijuana, cocaine, methamphetamine, heroin) and alcohol abuses during the last 12 months according to the judgement of the investigator
 21. Life expectancy < 12 months.

Dosage Form, Dose, and Route of Administration:

Edoxaban: 60, 30 and 15 mg provided as film coated tablets for oral use.

Subjects receive 60 mg edoxaban once-daily. A dose reduction (30 mg edoxaban once-daily) is determined for subjects with one or more of the following factors:

- Moderate or severe renal impairment (CrCL 15 - 50 mL/min)
- Low body weight: ≤ 60 kg (132 lbs),
- Concurrent use of P-gp inhibitors (please refer to local summary of product characteristics [SmPC] or to the Investigator Brochure [IB], as applicable);

In EU countries, according to SmPC concomitant use of edoxaban with cyclosporine, dronedarone, erythromycin, or ketoconazole requires dose reduction to 30 mg once-daily. Concomitant use of edoxaban with quinidine, verapamil, or amiodarone does not require dose reduction.

For low body weight (≤ 60 kg) present at randomization, the edoxaban dose is reduced permanently and even if the subject gains weight, the edoxaban dose remains reduced. The dose of edoxaban returns to the regular dosage regimen of 60 mg once-daily any time the subject no longer displays any of the other above mentioned factors.

After randomization and in subjects without dose reduction, if subject's:

body weight drops to ≤ 60 kg and the body weight change is > 10% of the subject's baseline body weight, then the

edoxaban dose is reduced (i.e. to 30 mg once-daily) permanently.

CrCL becomes 15 to 50 mL/min and the CrCL change is > 20% of the subject's baseline CrCL, then the edoxaban dose is reduced.

- = Develops the need for concomitant treatment with P-gp inhibitors (except quinidine, verapamil or amiodarone), then the edoxaban dose is reduced (i.e. to 30 mg once-daily).

The dose of 15 mg edoxaban once-daily is not indicated as monotherapy and is solely provided as part of transition from edoxaban 30 mg at the end of study (see Section 5.3.3).

VKA: Oral, VKA of choice, as pre-defined per country, with once-daily dosing for target INR between 2.0 to 3.0, inclusive.

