Subject clinical visits are planned at 1, 3, 6, 9 and 12 months after randomization. All subjects have telephone assessments at 2, 4, 5, 7, 8, 10 and 11 months after randomization. All information must be captured in the eCRF and study assessments are performed according to the visit schedule provided under appendix Section 17.9. All subjects are followed for 12 months irrespective of changes in the antithrombotic regimen. Clinical follow-up is only terminated at the explicit request of the subject. All subjects on either edoxaban or VKA at 12 months, have a contact planned 1 month after the end-of-treatment visit, to collect data on targeted concomitant medications, SAEs, and other events of interest. The overall duration of subject participation from screening through follow-up is therefore approx. 13 months.

The study organization, including the CEC, DSMB, Executive Committee and Steering Committee are described in appendix section 17.1. An independent DSMB reviews pertinent study data to protect the safety of the subjects participating in the study.

Figure 3.1 Study Design

• Edoxaban dose reduction to 30 mg once-daily if either CrCL \leq 50 mL/min, or body weight \leq 60 kg, or concomitant therapy with certain P-gp inhibitors. • Clopidogrel 75mg once-daily (or in the presence of a documented clinical need prasugrel [5 or 10 mg once daily] / ticagrelor [90 mg twice daily] may be used). •• VKA of choice with dosing for target international normalized ratio (INR) of 2.0 - 3.0 inclusiveASA (100 mg once-daily) for 1-12 months guided by the clinical presentation (ACS or stable coronary disease), and upon the CHA₂DS₂-VASc and HAS-BLED score.
§ Goal of at least 25% ACS.

AF, atrial fibrillation; ACS, acute coronary syndrome; PCI, percutaneous coronary intervention; ISTH, International Society on Thrombosis and Haemostasis; CRNM, clinically relevant non-major; h, hours; d, days.

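### The renal dose rules do not say consistently what happens when an edoxaban subject, reduced at randomization and later returned to 60 mg, falls back to CrCL 15-50 mL/min

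*Combined protocol and SAP*

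**What the plan says.** Section 5.3.1 contains three renal rules. The synopsis (Dosage Form, Dose, and Route of Administration) repeats them.

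- **At randomization.** 30 mg applies for "Moderate or severe renal impairment (calculated CrCL 15 - 50 mL/min". The test is on the absolute value, with no percentage condition.
- **Return.** The dose "returns to the regular dosage regimen of 60 mg once-daily any time the subject no longer displays any of the other above mentioned factors". No margin or confirmation is required, so a single CrCL just above 50 is enough if no other factor is present.
- **Later reduction.** The rule opens with "After randomization and in subjects without dose reduction, if subject's" and then requires that "CrCL becomes 15 to 50 mL/min and the CrCL change is > 20% of the subject's baseline CrCL". Both conditions must hold.

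The note to Figure 3.1 (Section 3.1) reads "Edoxaban dose reduction to 30 mg once-daily if either CrCL" is at or below 50 mL/min, or if another listed factor applies. It gives no 20% condition and no time point.

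The only baseline CrCL described is the last estimate given to the IXRS before randomization (Section 6.1.2), taken from local results after the index PCI (Section 6.1.1). Nothing resets it later. CrCL is rechecked at every on-site visit (Section 17.9 footnotes), so both a rise and a later fall would be seen. All edoxaban dose adjustments go through the IXRS.

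**The concern.** The first two rules depend on the current CrCL. The third depends on the current CrCL and on its distance from baseline. The combination is workable for a subject who starts above 50. A subject reduced for renal function on Day 1 has a baseline that is itself in the reduction range. After a return to 60 mg, measuring change from that baseline can leave the subject on 60 mg at the value that required 30 mg at randomization.

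Two sites, or a site and the IXRS programmer, could follow the text in good faith and reach different doses. The affected drug is an anticoagulant, half of whose absorbed dose is cleared by the kidney (Section 1.1.1.5). The rule operates in one arm only, and the primary endpoint is bleeding.

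**Working it through.** The plan states no figure on this point, so there is none to reproduce. The check applies the written rule. The CrCL values in the paths are illustrations, not document figures.

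**Reading A: the later rule covers anyone not currently reduced.** Let B be baseline CrCL (15-50) and C the CrCL after the return to 60 mg. Reduction requires 15 ≤ C ≤ 50 and a change of more than 20% of B. The text gives no direction, so there are two versions:

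- decrease only: (B − C)/B > 0.20, so nothing triggers from max(15, 0.8B) to 50;
- either direction: |C − B|/B > 0.20, so nothing triggers from max(15, 0.8B) to min(50, 1.2B).

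| Baseline B | 0.8B | 1.2B | No trigger, decrease only | No trigger, either direction |
|---|---|---|---|---|
| 50 | 40 | 60 | 40-50 | 40-50 |
| 45 | 36 | 54 | 36-50 | 36-50 |
| 40 | 32 | 48 | 32-50 | 32-48 |
| 30 | 24 | 36 | 24-50 | 24-36 |

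C = B always gives 0%, so a return to the Day 1 value never triggers reduction, for any baseline from 15 to 50 and in either version. Example paths:

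- 45 → 52 → 45: (45 − 45)/45 = 0%, no reduction.
- 40 → 52 → 33: (33 − 40)/40 = −17.5%, no reduction, although CrCL is below its Day 1 value.
- 40 → 52 → 31: (31 − 40)/40 = −22.5%, reduction.
- 40 → 52 → 49: (49 − 40)/40 = +22.5%, reduction if either direction counts, although 33 gives none.

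The reference value matters too. Measured against the CrCL at the return, 40 → 52 → 40 is (40 − 52)/52 = −23.1% and triggers, while 45 → 52 → 45 is (45 − 52)/52 = −13.5% and does not. The text does not provide for this reference.

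**Reading B: the later rule covers only subjects never reduced.** Baseline is then above 50 on the renal criterion, and the paths above fall outside the rule. No sentence in Section 5.3.1 explicitly says when a returned subject is reduced again. One can infer 30 mg from the return sentence, since 60 mg is tied to the absence of a factor. The Figure 3.1 note is compatible with that, but it could equally be shorthand for the Day 1 rule.

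**How many subjects.** The documents give no CrCL distribution or variability. An illustrative simulation under Reading A assumed true CrCL with mean 72 and SD 28 mL/min, within-subject CV of 7-15%, four visits after Day 1, and either no post-PCI dip or a transient 25% dip in 10% of subjects. About 4-11% of edoxaban subjects returned to 60 mg after a Day 1 renal reduction. About 3-6% later had at least one CrCL of 15-50 without re-reduction, roughly 20-45 of 750. These inputs do not remove subjects with low weight at randomization, whose reduction is permanent, so the count may be too high.

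**The case against.** The strongest reply is that the 20% condition is a deliberate buffer against small fluctuations, so different doses at the same CrCL on Day 1 and later are intended. For baselines above 50 this stands: a subject starting at 55 has a threshold of 0.8 × 55 = 44 and stays on 60 mg at 44-50. It does not settle the present case, because the reference value is already in the reduction range and the return step has no buffer.

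The second reply is that Reading B is natural and that the return sentence implies 30 mg whenever a factor is present. The text allows this, but does not say it.

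Three stronger conclusions are tempting and are not supported:

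- *The protocol definitely keeps these subjects on 60 mg.* That holds only under Reading A. The paradox of 49 against 33 for baseline 40 also needs change to count in both directions.
- *The fault is applied systematically at every site.* The IXRS specification is not in the documents and may already handle the case.
- *The bleeding comparison is materially biased.* No effect on the endpoint can be derived. As a deliberately severe illustration, suppose 6% of the arm had double the planned 18% one-year risk for the whole year. That adds 0.06 × 18 = 1.1 percentage points to the edoxaban rate, which works against edoxaban rather than flattering it. The doubling is an assumption, and most affected subjects would be exposed for only part of the year.

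**Conclusion.** The inconsistency is real and follows from the protocol's own wording. It is confined to edoxaban subjects with CrCL 15-50 at randomization, a later CrCL above 50, and no other reducing factor. Reading A leaves a defined range in which 60 mg continues at values that required 30 mg on Day 1. Reading B leaves no explicit rule. The Figure 3.1 note matches the Day 1 criterion but not the later one.

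That the reference is the pre-randomization value is an inference: only one baseline is described and no reset is given. The figure of 3-6% rests wholly on assumed inputs and shows only that the case need not be rare. The primary ITT analysis keeps its form, since Section 11.1.1 analyses by randomized regimen whatever the dose adjustments. What is at stake is the dose actually received and its consistency across sites.

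**What to change.** The sponsor should reconcile Section 5.3.1, the synopsis and the Figure 3.1 note so that they state:

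1. which subjects the post-randomization renal rule covers, and in particular whether it includes those reduced at randomization and later returned to 60 mg;
2. which CrCL value is the reference for the 20% change after such a return;
3. whether change means a decrease only or a change in either direction;
4. whether the Figure 3.1 note describes randomization only or the whole study.

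The sponsor should then confirm that the IXRS logic matches the reconciled text. The choice of dosing rule is left to the sponsor's clinical team. The cost is amendment wording and, if the IXRS differs, a logic change with testing. No new visits or samples are needed, because CrCL is already checked at each on-site visit.
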